- An increase in systolic blood pressure (SBP), mean arterial blood pressure (MAP) and orthostatic blood pressure (OBP).
- An increase in one or more of the following: TPR, CO, CBV, stroke volume (SV) and/or heart rate (HR).
- A decrease in the frequency of IDH and OH.

Primary and secondary endpoints

The primary endpoint for the study is BP (SBP, MAP and OBP)

Secondary endpoints are:

- Hemodynamic parameters: TPR, CO, CBV, SV and HR
- Electrolytes: Calcium, potassium and magnesium
- Frequency of IDH and OH

All endpoints are assessed as the difference between within-treatment changes during HD or HdF sessions when manipulating either dialysate temperature (35°C vs. 37°C) or DB concentration (30 mmol/L vs. 38 mmol/L).

Methodology

Study design

The study will be a single-blinded, randomized, controlled, crossover study with each participant being his or her own control (Figure 1). Participants will be blinded to the intervention and the order of the interventions will be random.

Participants will be randomized using bloc randomization. We will create two blocs (sequence 1 (Green) and sequence 2 (Yellow)) with 8 participants in each. The four dialysis sessions will be conducted on the same weekday each week, which results in a 1-week wash-out period with standard dialysis treatment between interventions.

Practical considerations

Dialysis machines, filters, and dialysate composition

Dialysis console Fresenius 5008F (Fresenius Medical Care, Bad Homburg, Germany) and HD or HdF filters regularly used for treatment of the patient will be used in all dialysis sessions.

The standard dialysate prescribed for each individual patient will be used in all dialysis sessions thereby maintaining similar composition regarding electrolytes such as sodium, potassium, calcium, magnesium and chloride. Bicarbonate concentration will only be adjusted in the sessions investigating low (30 mmol/L) and high (38 mmol/L) DB concentration, respectively. Dialysate will be prepared on-line by the dialysis machine. Blood flow rate and dialysate flow rate will be kept as usual and will remain equal in all sessions regardless of intervention. Ultrafiltration rate will be kept constant and equal in the two dialysis sessions. The same applies for the volume of substitution fluid in HdF.

Intradialytic restrictions regarding participants and their medications

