In order to standardize intradialytic conditions as much as possible and in order to avoid splanchnic redistribution of blood volume, the participants will be asked not to eat, drink, or sleep during the dialysis session. Throughout the study period medications affecting hemodynamics (e.g. blood pressure medications) will not be changed. Patients are encouraged not to deviate from their regular schedule in terms of timing or dosage of medication.

[figure not shown]

Figure 1: Study design

BP measurements

We will use the same automatic and validated BP device for all BP measurements (see Figure 2). The BP cuff will be chosen according to arm size and placed on the non-AV-fistula arm. The cuff should be positioned at the level of the heart, with the back and arm supported to avoid muscle contraction and isometric exercise-dependent increases in BP. Patient should be lying comfortably in a supine position for 5 minutes before beginning BP-measurements. Three BP measurements are recorded 1–2 min apart, and additional measurements only if the first two readings differ by >10 mmHg. BP is recorded as the average of the last two BP readings. The patient is not allowed to talk during the measurements.

OBP measurements

The patient will rest in bed for 5 minutes in the supine position, then HR (beats/min.) and BP (mmHg) are measured. The patient will then be asked to stand up beside the bed. BP and HR will be measured repeatedly with a 1-minute interval while standing for a minimum of 3 minutes. If BP declines at the third minute measurement, measurements can be continued for up to 10 minutes. The lowest BP while standing will be noted as the result for the orthostatic BP test.

Orthostatic hypotension (OH)

OH is defined as a reduction in SBP of at least 20 mmHg or in DBP of at least 10 mmHg within 3 minutes of standing (27).

Intradialytic hypotension (IDH)

IDH is defined as a decrease in systolic BP ≥ 20 mmHg or a decrease in MAP ≥ 10 mmHg associated with clinical events/symptoms (e.g. muscle cramps, abdominal discomfort, nausea or vomiting, dizziness or fainting, restlessness or anxiety, yawning or signing) and/or need for intradialytic interventions (Trendelenburg positioning, fluid administration, reduction in ultrafiltration rate, reduction of blood flow rate) or dialysis treatment cessation (28).

Before dialysis:

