As the participant arrives in the hemodialysis clinic, he/she will be weighed (kg) with usual clothing. He/she will be followed to a bed and asked to lie down in a supine position and then a standard 12-lead electrocardiogram (ECG) is recorded. Followed by a bioimpedance measurement using the Body Composition Monitor (BCM, Fresenius Medical Care) for determination of fluid status and body composition. Subsequently an orthostatic BP test will be performed.

The nurse will then prepare the patient for dialysis treatment and will manage insertion of dialysis needles in the AV-fistula. Furthermore, the nurse will connect the extra tubes needed for the Transonic device. Fragmin (standard dose) is administrated, and the dialysate temperature/dialysate bicarbonate is regulated according to randomization.

Before the dialysis session is started blood samples on infectious parameters and magnesium and an arterial blood gas will be drawn from the arterial cannula.

Time course - from the participant arrives to the participant leaves the dialysis clinic

[figure not shown]

Figure 2 An overview of the time course. It illustrates what will occur before, during and after dialysis.

During dialysis:

CO will be obtained by a previously validated ultrasound dilution technique using Hemodialysis Monitor HD03, Flow-QC tubing sets, and clip-on flow/dilution sensors from Transonic Systems Inc., Ithaca, NY, USA (29–32). The ultrasound sensors will be positioned on the arterial and venous Flow-QC tubing set using standard ultrasound gel to secure good contact. Access recirculation in the AV-fistula can invalidate CO-measurements. A built-in recirculation protocol will be used to check for access recirculation using injection of 10 mL isotonic saline into the venous blood line prior to the first CO-measurement. If recirculation is detected the dialysis needles will most likely be reinserted. CO will be measured in duplicate by injecting a bolus of 30 mL 37°C isotonic saline into the venous blood line within 5 seconds. If results deviate more than 15% a third measurement will be done. The mean of the two closest recordings will serve as the result. With the Transonic device intradialytic hemodynamic parameters are obtained at 10, 70, 130, 190, and 230 minutes. Patients will be lying in a supine position with the head elevated 20 degrees. Before each CO measurement HR and BP will be measured.

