Following the same time pattern as the Transonic measurements an arterial blood gas will be drawn from the arterial cannula.

Changes in relative blood volume (RBV) (%) during dialysis are monitored continuously by the module (blood volume monitor, Fresenius Medical Care) incorporated in the dialysis machine, which measures changes in RBV by measuring changes in hemoconcentration markers (hematocrit, hemoglobin or total blood protein concentration). Cumulative ultrafiltration volume (mL) is registered every 15 minutes during dialysis. Temperature and energy transfer in the arterial and

venous tubing will be recorded continuously by the blood temperature monitor mounted on the dialysis console (BTM, Fresenius Medical Care).

Generally, if a dialysis session is interrupted the participant will be given a replacement day on a corresponding weekday. In the event of IDH we will obtain a BP measurement and subsequently, the nurse will try to stabilize the patient with the necessary interventions.

After dialysis:

After dialysis an arterial blood gas will be taken from the arterial cannula for determination of the same parameters as before dialysis. Furthermore, a blood sample on magnesium will be drawn.

The hemodialysis nurse will stop the dialysis and remove the dialysis needles when the session is finished. Patients usually stay 10 minutes after removal of dialysis needles to ensure hemostasis/minimize the risk of bleeding from the AV-fistula. This time will be utilized for an OBP measurement, which will follow the same method as before dialysis. Lastly, the patient will be weighed and leaves the clinic.

Data from the dialysis session will be extracted from electronic patient journal, Therapy Data Management System (TDMS, Fresenius Medical Care) and Transonic HD03 Administrative Software (Transonic Systems Inc, Ithaca, NY). The mean arterial blood pressure (MAP), total peripheral resistance (TPR), and stroke volume (SV) are derived by the following equations:

$$\text{MAP} = \text{diastolic BP} + 1/3 \times (\text{systolic BP} - \text{diastolic BP})$$

$$\text{CO} = \text{SV} \times \text{HR} = \text{MAP}/\text{TPR}$$

Central blood volume (CBV) is defined as the volume of blood in the heart, lungs and great vessels and is estimated with the Transonic device based on the CO measurement as previously described (29).

Dialytic Kt/V urea will be estimated by using Daugirdas formula (33) and urea reduction ratio will be calculated.

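### Cardiac output, TPR, SV and CBV have no reading before the allocated dialysate setting takes effect, so their change scores start 10 minutes into treatment

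*Protocol*

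**What the plan says.** Under Primary and secondary endpoints, the protocol states: "All endpoints are assessed as the difference between within-treatment changes during HD or HdF sessions". The Statistical analysis section applies this to hemodynamics and solutes alike: a delta within each session, then the difference of the two deltas, tested with a paired t-test. Neither section names the time point that serves as baseline.

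Under Before dialysis, the sequence is as follows. The patient is weighed, and the ECG and bioimpedance are recorded. Then: "Subsequently an orthostatic BP test will be performed". In that test the patient rests supine, "then HR (beats/min.) and BP (mmHg) are measured". Needling and tubing follow, and "the dialysate temperature/dialysate bicarbonate is regulated according to randomization". The last step before start is sampling: "Before the dialysis session is started blood samples on infectious parameters and magnesium and an arterial blood gas will be drawn from the arterial cannula". No CO reading is listed in this phase.

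Under During dialysis: "With the Transonic device intradialytic hemodynamic parameters are obtained at 10, 70, 130, 190, and 230 minutes". HR and BP are taken before each CO measurement, and an arterial blood gas is drawn on the same schedule.

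Under After dialysis, MAP, "total peripheral resistance (TPR), and stroke volume (SV) are derived by the following equations", the second equation linking CO to SV, HR, MAP and TPR. CBV is likewise estimated by the Transonic device from the CO measurement.

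**The concern.** A change score isolates a treatment effect when its starting value is untouched by treatment. For CO, TPR, SV and CBV no such value exists in any session. The only candidate, the 10-minute reading, follows 10 minutes of 35 vs 37°C, or of 30 vs 38 mmol/L. Whatever between-setting difference has developed by then is subtracted from the later difference. Randomising the order of sessions does not remove this, because the baseline itself can differ by treatment.

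These four variables are the ones meant to explain how any blood pressure effect arises. At stake is understating how CO, TPR, SV and CBV respond, with the understatement greatest where the response is fastest.

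**Working it through.** **The plan's own figure.** For the SBP contrast the inputs are a difference of 10 mmHg, SD 12 mmHg, two-sided alpha 0.05 and power 0.80. Exact noncentral-t power for the paired (one-sample) test is 0.788 at n = 13 and 0.822 at n = 14, so the stated 14 reproduces, and 14 + 2 = 16. This concerns SBP only and is not disturbed by the point made here.

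**Which endpoints have a value before the setting acts.**

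| Endpoint | Pre-treatment value? | Source |
|---|---|---|
| SBP, MAP, orthostatic BP | Yes | Orthostatic test before needling |
| HR | Yes | Same test |
| Magnesium | Yes | Blood sample before start |
| Calcium, potassium | Yes, if taken from the blood gas (the protocol does not assign analytes to tubes) | Blood gas before start |
| CO | No | Transonic, first at 10 min |
| TPR, SV | No | Calculated from CO |
| CBV | No | Estimated from CO |

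Four of the five hemodynamic secondary endpoints are therefore affected.

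**What the contrast estimates.** Let E(t) be the mean between-setting difference at time t, with E(0) = 0. The difference of changes from 10 minutes to t estimates E(t) − E(10). At the last reading, the share of the effect removed is E(10)/E(230).

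**Size, under assumed curves.** The documents give no time course, so the curves below are assumptions.

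- Linear build-up: 10/230 = 0.043.
- Exponential build-up, E(t) proportional to 1 − exp(−t/τ): share = (1 − exp(−10/τ)) / (1 − exp(−230/τ)).

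| τ (min) | Numerator | Denominator | Share removed |
|---|---|---|---|
| 120 | 0.080 | 0.853 | 9% |
| 60 | 0.154 | 0.978 | 16% |
| 30 | 0.283 | 1.000 | 28% |
| 15 | 0.487 | 1.000 | 49% |

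A shorter τ would remove more.

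**For scale only.** No effect size or SD is given for these four variables. If one of them had the standardised effect assumed for SBP (10/12) with n = 14 and an unchanged SD, power would fall from 0.82 to 0.79 with 4.3% removed and to 0.55 with 28% removed.

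**The case against.** The strongest reply has four parts.

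**The dilution method needs a running circuit.** A recirculation check and HR/BP must also precede the first CO measurement, so a reading before any flow is impossible. This stands, and it explains why the first reading is not at time zero. It does not explain why the allocated setting must already be active at that reading.

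**The baseline is not named, and an SAP may settle it.** This is partly right. An SAP could choose to compare levels as well as changes, and the recorded 10-minute values allow an early difference to be examined. But the protocol already fixes the change contrast for all endpoints, and no SAP can supply a reading that was never taken.

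**The harm is conditional.** This stands. Attenuation needs an effect within 10 minutes of the same sign as the later one, and the documents do not show that there is one.

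**Changing the procedure has a price.** This stands too. A setting change within the session departs from the fixed temperature comparison set out in the Summary of the background, and the new setting takes time to take effect.

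A reader might also infer that calcium, potassium and acid-base status, as proposed mediators, are measured over a different window from the hemodynamics. The documents do not support that for blood-gas variables: gases follow the Transonic schedule, and the seven gases per session fit one before, five during and one after. These variables can be matched to the 10–230 minute window. Only magnesium, described as drawn before and after dialysis, cannot.

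**Conclusion.** The point holds for CO, TPR, SV and CBV, all secondary endpoints. Followed as written, the plan gives them an on-treatment baseline, and their contrast estimates E(t) − E(10). The schedule is certain from the text. The size of the loss is not: about 4% to 49% of the 230-minute effect over the assumed curves, with no figure in the documents to narrow it. Figure 2 was not available; a baseline CO shown there would conflict with the listed times.

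Two stronger readings are tempting and should be resisted. A reader might infer that every within-session change is compromised. That is not so: BP, orthostatic BP, HR and electrolytes have pre-dialysis values, and the sample size rests on SBP. It would still help to state whether the BP and HR changes start from the pre-dialysis or the 10-minute value. A reader might also infer that the schedule alone could produce a null result for TPR or CO. Nothing in the documents supports that. Across the assumed range at least half the effect remains, so the consequence is attenuation and lower power.

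**What to change.** **Preferred, if the investigators find it feasible.** In the session procedure, record the first CO/CBV/HR/BP set with the circuit running on a setting common to both sessions of a pair, which is for the investigators to choose. Then apply the allocated setting, and name that set as the baseline for CO, TPR, SV and CBV. No measurement is added. The cost is roughly 10 of 240 minutes (about 4%) of exposure to the allocated setting, a setting change within each session, and some time for it to take effect.

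**If conduct stays as it is.** State that changes in these four endpoints are changes from 10 minutes on treatment. Alongside the difference of changes, add paired between-session comparisons of the 10-minute values and of the levels from 70 to 230 minutes. Randomised order permits both, and no new data are needed. An early effect would then be visible instead of being subtracted out unseen. The cost is a little more analysis and the lower precision to be expected of levels, which keep the session-to-session variation that change scores remove. That matters with 14 to 16 participants, so the levels should accompany the changes and not replace them.

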Dialysis sessions are expected to last 30 minutes longer than usual, and patients will be informed of this before agreeing to participate.

Statistical considerations

Statistical analysis

Within-treatment changes in hemodynamics and plasma concentrations of solutes will be calculated as differences (delta values), whereas between intervention comparisons (control vs. intervention) are performed by calculating the difference between within-treatment changes (“delta-delta values”). A two-tailed, paired Student’s t-test with no difference between the two treatments as the null hypothesis will be used to compare the two interventions. Statistical significance (α - level) will be set to 0.05. The paired t-tests require data to conform to a normal distribution. If this is not the case,

a logarithmic transformation of data can be performed to achieve a normal distribution. Alternatively, a non-parametric test (Wilcoxon Signed Rank test) can be performed to compare changes in relevant delta-values between the two groups.

Power and sample size

For estimation of standard deviation (SD) we used SBP measurements obtained before and after dialysis from 30 randomly selected patients undergoing HD or HdF treatment in the Dialysis Clinic at Aarhus University Hospital. Two treatment sessions were analyzed for each patient. The within treatment changes in SBP and mean differences between within-treatment changes in SBP (delta-delta values) and corresponding SD's were calculated, which yielded SD = 23 mmHg for the difference between within-treatment changes in SBP. This SD reflects non-standardized conditions in terms of dialysis treatment settings and BP-measurements in randomly selected patients not meeting the strict in-/exclusion criteria of the present study. Therefore, assuming a lower SD under standardized conditions we decided that SD = 12 mmHg was a reasonable estimate for the present study. Sample size calculation with Stata/IC 16.1 (StataCorp, [name], USA) using analysis for a one-sample mean test (t-test), assuming a minimal detectable difference in means (mean difference between the two within-treatment changes in systolic BP) = 10 mmHg; SD = 12 mmHg; two-sided significance level (alpha) = 0.05; power=0.80 resulted in 14 participants. However, to account for dropout of two participants, a sample size of 16 was chosen.

Study participants

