Participants might feel slightly uncomfortable during intervention with LTD in terms of cold sensation or related symptoms (10), but could on the other hand also feel less fatigue and more energetic according to previous studies examining LTD (34,35).

Participant exclusion and discontinuation of the study

Should any serious known or unknown side effects or complications occur during the study, the study session will be discontinued, and the participant will receive treatment from a dialysis nurse or a medical doctor if deemed necessary. Following this, the investigators of the study in consultation with the patient will decide if the patients is to be excluded from the study or offered a replacement session on a corresponding weekday.

If blood samples obtained on a given study session show signs of infection, the data obtained in this study session will be deemed invalid and will not be used in the study. Strong suspicion of infection will be handled as per usual in the hospital setting and can potentially lead to hospitalization for further investigation. Once the infectious state has receded, the patient can continue in the study via

a replacement day on a corresponding weekday. In the case of protracted illness or hospitalization, the patient will be excluded from the study.

Blood sampling and handling of biological material

Eleven blood samples will be taken from the arterial blood line via the AV-cannula used for dialysis treatment. Four of the samples will be regular blood samples of 3-4 mL, whereas 7 of the samples will be arterial blood gases of 1 mL. Thus, per session 22 mL blood per participant is collected which adds up to a total of 88 mL for the entire study period. The purpose of this is to determine several essential parameters:

- Electrolytes such as calcium, magnesium, and potassium
- Acid-base status: pH, standard bicarbonate, standard base excess
- Hemoglobin, hematocrit
- Urea for the determination of Kt/V and URR.
- White cell count and C-reactive protein in the first blood sample in order to confirm the absence of infection

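### Does generally replacing interrupted sessions, with no exception for hypotension, bias the blood pressure and IDH comparisons?

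*Protocol*

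**What the plan says.** All places are in the protocol.

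- **Methodology, During dialysis:** "Generally, if a dialysis session is interrupted the participant will be given a replacement day on a corresponding weekday". No cause of interruption is named or excepted. The next sentence deals with hypotension separately: "In the event of IDH we will obtain a BP measurement and subsequently, the nurse will try to stabilize the patient".
- **Intradialytic hypotension (IDH):** a fall in systolic or mean pressure counts when it comes with symptoms or with certain interventions. The list of interventions ends with "reduction in ultrafiltration rate, reduction of blood flow rate) or dialysis treatment cessation".
- **Primary and secondary endpoints:** "The primary endpoint for the study is BP (SBP, MAP and OBP"). The secondary endpoints include the "frequency of IDH and OH".
- **Statistical analysis:** "between intervention comparisons (control vs. intervention) are performed by calculating the difference between within-treatment changes", followed by a paired t-test.
- **Participant exclusion and discontinuation of the study:** after a serious complication the investigators, together with the patient, decide between exclusion and being "offered a replacement session on a corresponding weekday". For a session with signs of infection, "the data obtained in this study session will be deemed invalid and will not be used in the study".
- **Study participants, Table 2:** patients with earlier interrupted or prematurely ended dialysis are not eligible.

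No section says whether the interrupted session or its replacement is analysed after an interruption for hypotension.

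**The concern.** An interruption in this trial may be an outcome. Stopping dialysis after a pressure fall can satisfy the IDH definition, and blood pressure is the primary endpoint. The paired analysis needs one within-session change per participant and condition, and a completed replacement is the obvious session to supply it. If analysts used it and set the stopped session aside, the worst pressure falls would be redrawn and their IDH events would disappear from the count.

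The direction depends on how sessions come to be stopped. If the low setting does protect pressure, and a given fall leads to stopping equally often in both conditions, more control sessions are redrawn and the contrast shrinks. If staff stop more readily under the low setting, it can grow. With no true effect and equal stopping there is no bias. What is at stake is a distorted systolic difference in a small trial, and an IDH comparison built on very few events.

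**Working it through.** **1. The plan's own figure.** Power and sample size gives a difference of 10 mmHg, SD 12 mmHg, two-sided alpha 0.05 and power 0.80. Exact one-sample t-test power (noncentral t) is 0.788 at n = 13 and 0.822 at n = 14. The stated 14 reproduces, and 14 + 2 = 16. The concern does not touch the sample size.

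**2. Model for the shift in the systolic difference.** The protocol gives no mean pressure fall and no stopping rate, so the following are assumptions:

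- mean systolic change of −15 mmHg in control and −5 mmHg in the low setting, a true difference of 10;
- per-session SD s = 12/√2 = 8.49, or 23/√2 = 16.26 using the SD observed in the clinic sample;
- between-patient SD w of 0 or 10, and t = √(s² + w²);
- a session with a fall of at least 20 mmHg is stopped with probability f and replaced once, and only the replacement is analysed.

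For a condition with mean m, replacement raises the expected change by

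shift(m) = f × (s²/t) × φ((−20 − m)/t),

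where φ is the standard normal density. The analysed difference is 10 − shift(−15) + shift(−5).

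**3. A plausible stopping rate.** The Background puts IDH prevalence at 10–12%. Read as a per-session risk, with at most 25% of IDH sessions ending early, the share of control sessions stopped is at most 0.12 × 0.25 = 3%. Setting f so that 3% of control sessions are stopped, with the same f in both conditions:

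| SD | w | Control sessions with fall ≥ 20 | f | Shift, control | Shift, low | Analysed difference |
|---|---|---|---|---|---|---|
| 12 | 0 | 27.8% | 0.108 | 0.31 | 0.08 | 9.77 |
| 12 | 10 | 35.2% | 0.085 | 0.17 | 0.10 | 9.92 |
| 23 | 0 | 37.9% | 0.079 | 0.49 | 0.34 | 9.85 |
| 23 | 10 | 39.7% | 0.076 | 0.40 | 0.31 | 9.90 |

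The shift is about 0.1 to 0.2 mmHg. Simulated power at n = 14 with SD 12 is 0.81 to 0.82, against 0.82 with full data.

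**4. The pessimistic end.** With f = 0.50 and SD 12 the difference falls to 8.9–9.6 mmHg and power to 0.78 at worst. But between 28% and 40% of control sessions have a qualifying fall in this model (both SDs), so f = 0.50 stops 14% to 20% of them. That is more than the whole 10–12% IDH prevalence, in patients screened for no history of interruption.

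**5. Direction.** With f = 0.10 in control and 0.25 in the low setting the difference is 9.9–10.1 (SD 12) or 10.4–10.5 (SD 23). The sign is therefore not fixed.

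**6. IDH count.** Take control risk p = 0.10 to 0.12, half of that in the low setting, and 16 participants. The expected number of IDH sessions in control is 16 × p = 1.6 to 1.9. If a share f of them is replaced and only the replacement counts, the recorded rate is p(1 − f) + p·f·p, and 16 × p × f × (1 − p) events are lost:

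- p = 0.10, f = 0.05: 16 × 0.10 × 0.05 × 0.90 = 0.07;
- p = 0.12, f = 0.25: 16 × 0.12 × 0.25 × 0.88 = 0.42.

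The low setting loses about half as many. The absolute difference shrinks by 4% to 21%. The ratio barely moves: at p = 0.10 and f = 0.25 it is 0.0381/0.0775 = 0.49 instead of 0.50.

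**The case for a change.** The strongest case for acting is that the replacement rule is trial conduct, fixed in the protocol, and not something an SAP can undo. The protocol states what happens to the data of one kind of replaced session (infection) but not of the kind closest to its endpoints. The choice between exclusion and replacement after a serious complication is made case by case and could also follow the outcome. With fewer than two IDH sessions expected per condition, relabelling one would be visible. A few sentences written before the data are seen would remove the doubt at almost no cost.

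Much of this stands as description. The silence is real, the events are few, and a sentence of clarification would be harmless. It does not show a fault in the plan:

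- Replacing a session does not discard its data. The only discard rule is for infection, and the pressure reading required at an IDH event gives no hint that such events are to be dropped.
- The stated response to IDH is to stabilise the patient. Only hypotension that actually ends a session reaches the replacement rule.
- The rule is worded as a general practice, and exclusion is an alternative after serious complications. It is not a mandate for every interruption.
- Counting IDH does not need one completed session per condition, so an analyst has no reason to ignore an event in a stopped session.
- For the pressure change itself, a full-length replacement is a defensible source. The alternative, the last reading before the stop, may come well before 230 minutes, may not follow the standard measurement procedure, and may leave no post-dialysis orthostatic value. Either choice has a cost.

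**Conclusion.** The concern does not call for a change. The protocol leaves open which session is analysed after an interruption for hypotension. It does not fix a biased analysis, because the bias arises only if the stopped session is ignored, and nothing says that it will be. An analyst can fill the gap sensibly by counting an IDH event under the condition assigned to that session, whether or not a replacement follows, and by reporting replaced sessions by condition and cause. The event reading needed for this is already required.

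Even if only replacements were used, the systolic difference would move by about 0.1 to 0.2 mmHg out of 10, and 0.07 to 0.42 IDH events would be lost in the control condition. This assumes about 3% of control sessions stopped and the same stopping probability in both conditions for the systolic figure, and 5% to 25% of IDH sessions ending early for the IDH figure. It also treats the general prevalence of 10–12% as a per-session risk. Because patients with earlier interruptions are excluded, the real figures are probably lower. The direction would be uncertain if stopping differed between conditions.

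### Optional improvement: order is randomised in two sequences, but the fixed paired t-test has no sequence term; adding one costs about half a power point at 7+7

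*Protocol*

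**What the plan says.** Under Study design the protocol makes order random: "We will create two blocs (sequence 1 (Green) and sequence 2 (Yellow)) with 8 participants in each". It adds that "The four dialysis sessions will be conducted on the same weekday each week", with a one-week wash-out on standard dialysis between interventions.

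Under Statistical analysis, the between-intervention comparison is "performed by calculating the difference between within-treatment changes". The test is a two-tailed paired Student's t-test, "with no difference between the two treatments as the null hypothesis will be used to compare the two interventions", at the 0.05 level. If the data are not normal, a logarithmic transformation or a Wilcoxon signed rank test may be used. Neither the test nor the fallbacks refer to sequence or period.

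Under Power and sample size, a one-sample t-test calculation (difference 10 mmHg, SD 12 mmHg, 80% power) gives 14 participants, raised to 16 to allow for two dropouts.

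The primary endpoint is blood pressure in three forms (SBP, MAP and orthostatic BP), and the comparison is made separately for temperature and for bicarbonate.

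**The concern.** The design creates and balances a factor, the order of treatments, that the stated analysis does not use. If the intradialytic change in BP shifts between a participant's earlier and later session for reasons unrelated to treatment, the shift raises the delta-delta in one sequence and lowers it in the other.

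With equal sequences the shift cancels from the mean but remains in the variance of the paired test, which widens the confidence interval and lowers power. With unequal sequences part of it also stays in the estimate.

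False-positive risk is not at stake. What is at stake is precision, in a trial sized for 14 completers with power only slightly above its 80% target.

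**Working it through.** **Inputs from the protocol.** Difference δ = 10 mmHg, SD σ = 12 mmHg, two-sided α = 0.05, 14 completers, 16 randomised (Power and sample size); two sequences of 8 (Study design). The SD of 23 mmHg from the clinic data is used as a sensitivity value.

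**Assumed, not in the protocol.** A period effect x of 0 to 10 mmHg on the change in SBP, entering the delta-delta as +x in one sequence and −x in the other:

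delta-delta = δ ± x + normal error with SD σ.

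**Step 1: reproduce the plan's figure.** For the one-sample t-test, the noncentrality is (δ/σ)√n with n−1 degrees of freedom. At n = 14 it is (10/12)√14 = 3.118 with 13 df, giving power 82.2%. At n = 13 power is 78.8%. The smallest n reaching 80% is 14, as stated.

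**Step 2: cost of the term when x = 0.** The adjusted estimate is the mean of the two sequence means, with SE = σ√((1/n₁ + 1/n₂)/4) and n−2 df.

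| Completers | SE, mmHg | Paired power | With sequence term | Cost, points |
|---|---|---|---|---|
| 7+7 | 3.207 | 82.2% | 81.6% | 0.5 |
| 8+8 | 3.000 | 87.6% | 87.2% | 0.3 |
| 8+6 | 3.240 | 82.2% | 80.8% | 1.3 |

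The required number stays at 14.

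**Step 3: power when x is not 0.** The paired test's variance estimate then follows a scaled noncentral chi-square distribution, and power was integrated over it. The adjusted analysis does not depend on x.

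| Completers | x = 0 | 2.5 | 5 | 10 mmHg | With term, any x |
|---|---|---|---|---|---|
| 7+7, paired | 82.2% | 80.9% | 77.0% | 60.9% | 81.6% |
| 8+8, paired | 87.6% | 86.6% | 83.4% | 69.5% | 87.2% |

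- The two analyses have equal power at x of about 1.6 mmHg (7+7) or 1.4 mmHg (8+8).
- Paired power falls below 80% once x exceeds about 3.2 mmHg (7+7) or 6.6 mmHg (8+8).
- The mean 95% CI half-width of the paired test at 7+7 is 6.8, 7.4 and 9.0 mmHg at x = 0, 5 and 10. With the term it is 6.8 mmHg throughout.

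**Step 4: unequal completers.** The bias of the paired estimate is x(n₁ − n₂)/n. At 8+6 this is 2x/14 = x/7, or 0.4, 0.7 and 1.4 mmHg at x = 2.5, 5 and 10. At x = 5, paired power is 82.7% or 70.5% depending on the direction of the bias, against 80.8% with the term.

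**Step 5: validity of the paired test.** Type I error at 7+7 is 5.0, 3.5 and 1.2% at x = 0, 5 and 10. At 8+6 it is 4.7, 3.9 and 1.9% at x = 2.5, 5 and 10. The test is conservative, never liberal, in these settings.

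**Step 6: larger SD.** With σ = 23 at 7+7 and x = 0, power is 32.6% paired and 32.2% with the term. The term therefore has no bearing on whether 12 or 23 is the better planning value.

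**The case against.** The strongest case against is that nothing is wrong. The test is valid, it matches its own sample-size calculation, and a covariate of this kind is often settled in a statistical analysis plan. The specific arguments are these.

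- **No period effect is documented.** Several provisions work against one: same-weekday sessions, "Ultrafiltration rate will be kept constant and equal in the two dialysis sessions", and "Throughout the study period medications affecting hemodynamics (e.g. blood pressure medications) will not be changed". For imbalance, "if a dialysis session is interrupted the participant will be given a replacement day on a corresponding weekday". This stands: with no period effect the term slightly lowers power, and at 2.5 mmHg the gain at 7+7 is only 0.7 points (81.6 − 80.9). The large losses need a period effect as big as the treatment difference itself.
- **The reading of SD 12.** It is treated above as the SD around the sequence means. If it is instead the total SD including the period effect, paired power at 7+7 does not fall below target: 82.6% at 2.5 and 84.3% at 5 mmHg. The term still adds power (83.4% and 88.7%). The 3.2 mmHg threshold therefore depends on the first reading, which is reasonable because the clinic SD describes ordinary repeat sessions around their mean.
- **The half-point cost belongs to 7+7.** If two of 16 drop out at random, 7+7 has probability 8×8/120 = 53% and 8+6 has 47%, so the expected cost is 0.53×0.5 + 0.47×1.3, about 0.9 points. At 8+6 with a 2.5 mmHg effect, paired power is 83.6% or 78.0% by direction, averaging the same 80.8% as with the term. The gain there is removal of the 0.4 mmHg bias, not power.
- **Figure 1 is not available here.** If Green and Yellow only swap which intervention comes first, rather than the low/high order within each, a sequence term is not a period term. This is a real condition on the proposal.
- **The Wilcoxon fallback would still ignore sequence.** True; the gain is lost if that fallback is used.

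These points limit the size of the benefit. They do not remove it, because the protocol names a specific test rather than leaving the choice open.

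**Conclusion.** The point holds as an optional improvement. The paired t-test is valid and conservative, and the sample size of 14 is correct for it. A sequence term protects precision against a period effect at a price of one degree of freedom: 0.3 to 1.3 power points, with power remaining above 80% at 7+7, 8+8 and 8+6 under the protocol's SD of 12. It starts to pay at a period effect of about 1.6 mmHg (7+7), well below the 10 mmHg the trial is sized to detect, and at 5 mmHg it is worth 4.6 points at 7+7 (81.6 − 77.0, from unrounded figures 81.63 − 76.96 = 4.67).

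The conclusion rests on an assumed period effect, on reading SD 12 as residual variation, and on the low/high order reversing between the two sequences. Confidence is moderate, because the benefit depends on an effect whose size the protocol does not give.

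**What to change.** In Statistical analysis, for each intervention (temperature, bicarbonate) and each BP endpoint (SBP, MAP, orthostatic BP), regress the participant's delta-delta (low minus high) on sequence as randomised, coded +1 and −1. Report the intercept as the treatment difference with its 95% CI. Keep the paired t-test as a sensitivity analysis; the named fallbacks can remain.

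Before adopting this, confirm from Figure 1 that the low/high order reverses between Green and Yellow within each intervention. If a statistical analysis plan already includes the term, bring the protocol wording into line with it.

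The cost is a change of analysis wording and one residual degree of freedom (12 instead of 13 at n = 14; 14 instead of 15 at n = 16). No new data, participants or procedures are needed.
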